### **d. Definition of MTD**

The MTD is the highest dose at which no more than 1 of the 6 patients in each cohort of the dose escalation phase develops a DLT. If 2 or more of 6 patients in each cohort of the dose escalation phase develop DLT at a particular dose level, that dose has exceeded the MTD.

### **3.1.2 Dose Expansion Phase**

The objectives of the dose expansion phase are to evaluate the anticancer activity and safety of fruquintinib at the RP2D determined at the end of the dose escalation phase, as described in Section 2.2.

Once the RP2D is determined, patients may enroll into one of the following cohorts and will receive fruquintinib at the RP2D.

- Cohort A: Patients with advanced, refractory solid tumors of any type
- Cohort B: Patients with refractory mCRC who have progressed on all standard chemotherapies and relevant biologics and have also progressed on, or had intolerable toxicity with, at least 1 FDA-approved third-line therapy (TAS-102 or regorafenib).

- Cohort C: Patients with refractory mCRC who have progressed on all standard chemotherapies and relevant biologics and *have not* received prior TAS-102 or regorafenib.
- Cohort D: Patients with hormone-receptor positive (ER+ and/or PR+)/Her2-metastatic breast cancer who have progressed on at least two line of prior systemic therapy.
- Cohort E: Patients with advanced triple negative breast cancer (TNBC) who have progressed on at least one cytotoxic therapy in the metastatic setting.

Detailed patient inclusion and exclusion criteria for each expansion cohort is described in Sections [4.1](#) and [4.2](#).

The safety of all enrolled patients will be closely monitored from the first day of fruquintinib dosing until 30 days after the last dose. All SAEs should be reported from the day the informed consent form (ICF) is signed through 30 days after last dose regardless of relationship to study drug. All AEs will be graded in accordance with the NCI CTCAE v4.03.

Tumor response will be assessed according to RECIST Version 1.1 at screening and at study visits according the Schedule of Events ([Appendix A](#)). Confirmation of CR and PR is required at no less than 4-week intervals between the date of initial response and the confirmation assessment date.

Patients will be followed until death or study completion ([Appendix A](#)).

### 3.2 Sample Size

Approximately 128 patients will be enrolled in this dose escalation/dose expansion study. Approximately 12 patients will be enrolled in the dose escalation phase, and approximately 116 additional patients (6 with advanced solid tumors of any type, 40 with refractory mCRC who progressed on TAS-102 and/or regorafenib, 40 with mCRC who had not received TAS-102 or regorafenib, 15 with refractory HR+/HER2- mBC, and 15 with advanced, refractory TNBC) will be enrolled in the dose expansion phase.

### 3.3 Investigational Site

Approximately 12 sites will participate in the study.

### 3.4 Safety Review Committee

A Safety Review Committee (SRC) will be established under a charter to conduct safety data review and to determine the next step for dose escalation. Safety monitoring and evaluation for dose escalation decisions will be carried out by the SRC upon completion of the of the DLT observation period of the last patient in each cohort. The SRC is chaired by the Sponsor's fruquintinib Clinical Program Leader; members will include the principal investigators (PIs), the Sponsor's PK scientist, medical monitor, and the CRO's medical monitor.

Dose escalation decisions are based on AE and PK data from this ongoing trial, as well as consideration of safety and PK data at comparable drug exposure from patients in

previously conducted clinical trials in China.

Regular safety data review will be conducted at pre-defined intervals and at the end of the DLT observation period (ie, first treatment cycle) of each dose cohort. Safety and PK data from all enrolled patients will include laboratory test results, AEs, electrocardiogram (ECG) results, and PK data.

### 3.5 Study Early Termination

Hutchison MediPharma has the right to stop the study at any time. The reasons for stopping the study may include, but are not limited to:

- The incidence or severity of AEs in this or other studies indicates a potential health hazard to patients.
- Patient enrollment is unsatisfactory.

### 3.6 Patient Discontinuation

All study participants have the right to withdraw from the study at any time. The investigator has the right to discontinue a patient from the study for any medical condition that the investigator determines may jeopardize the patient's safety if he or she continues in the study and for reasons of non-compliance (eg, missed doses, visits) or pregnancy or if the investigator determines it is in the best interest of the patient. Any patient who discontinues treatment should be encouraged to return to the study site for a treatment completion visit. See [Appendix A](#) for the assessments that are to be performed for patients who prematurely withdraw from the study during the treatment period. The primary reason for discontinuation must be recorded on the appropriate Case report form (CRF).

#### **Study drug treatment will end if a patient meets any of the following 3 criteria:**

1. Disease progression (according to RECIST Version 1.1) unless there is reasonable evidence of clinical benefit to justify continuation on the study treatment. The decision that the patient should continue treatment should be made by the investigator in consultation with the Sponsor. The disease progression date is the date when radiological disease progression is first reported according to RECIST Version 1.1 criteria;
2. Death;
3. End of this study.

#### **Early discontinuation of study treatment will occur if any of the following criteria is met:**

1. Patient withdrawal of consent;
2. Intolerable toxicity;
3. Poor patient compliance;
4. Use of other antitumor treatment during the study;
5. Pregnancy occurred during the study treatment period;
6. Patient is lost to follow-up;

7. Treatment discontinuation is in the best interest of the patient based on the assessment of the investigator and the Sponsor.

### **3.7 End of Study**

End of the study is defined as the last visit of the last patient.

## 4 PATIENT SELECTION

Patients with locally advanced or metastatic solid tumors of any type, and patients with refractory mCRC for whom approved therapy either does not exist or has proven to be ineffective or intolerable are eligible to participate in this study. Patients will undergo a screening period of up to 4 weeks, during which they will be assessed for compliance with the inclusion and exclusion criteria as outlined below.

### 4.1 Inclusion Criteria

To be eligible to participate in the study, patients must meet **all** of the following Inclusion Criteria:

1. Fully understand the study and voluntarily sign the ICF;
2.  $\geq 18$  years of age;
3. Body weight  $\geq 40$  kg;

#### 4. Dose Escalation Phase:

Histologically or cytologically documented, locally advanced or metastatic solid malignancy of any type (except squamous NSCLC) that has progressed on approved systemic therapy, and for whom no effective therapy or standard of care exists.

#### Dose Expansion Phase:

**Cohort A:** Histologically or cytologically documented, locally advanced or metastatic solid malignancy of any type (except squamous NSCLC), that has progressed on approved systemic therapy, and for whom no effective therapy or standard of care exists.

**Cohort B:** Histologically or cytologically documented adenocarcinoma of the colon or rectum that has progressed on, or had intolerable toxicity to, at least 1 FDA-approved third-line systemic therapy (TAS-102 or regorafenib). Treatment failure is defined as disease progression during or within 3 months after the last dose of standard therapy, or discontinuation of standard therapy because of unacceptable toxicity. Patients must also have been previously treated with fluoropyrimidine-, oxaliplatin-, and irinotecan-based chemotherapy, an anti-VEGF biological therapy, and, if RAS wild type, an anti-EGFR therapy.

Eligibility also requires knowledge of tumor RAS status (wild-type or mutant) as reported by investigators.

**Cohort C:** Histologically or cytologically documented adenocarcinoma of the colon or rectum. Patients must have progressed on, or had intolerable toxicity to, at least 2 prior regimens of standard chemotherapy, but *must not* have received prior TAS-102 or regorafenib. Treatment failure is defined as disease progression during or within 3 months after the last dose of standard therapy, or discontinuation of standard therapy because of unacceptable toxicity. Prior therapy could have included adjuvant chemotherapy if a tumor had recurred within 6 months after the last administration of

treatment. Patients must have been previously treated with fluoropyrimidine-, oxaliplatin-, and irinotecan-based chemotherapy, an anti-VEGF biological therapy and, if RAS wild-type, an anti-EGFR therapy

Eligibility also requires knowledge of tumor RAS status (wild-type or mutant) as reported by investigators.

### **Cohorts D and E:**

Her2-negative metastatic breast cancer, with Her2-negative defined as immunohistochemistry (IHC) 0, 1+, or 2+. If IHC 2+, a negative in situ hybridization (FISH, CISH, or SISH) test is required by local laboratory testing.

- a. **Cohort D only:** Histologically- or cytologically-confirmed hormone-receptor positive (ER+ and/or PR+) breast cancer, by local assessment.  
OR
  - b. **Cohort E only:** Histologically- or cytologically- confirmed triple negative breast cancer with ER-negative, PR-negative tumors as defined by local criteria.
5. Hormone receptor positive mBC patients must have progressed on at least 2 lines of prior systemic therapy, including hormonal therapy or chemotherapy. However, patients may not have received more than 3 prior lines of cytotoxic chemotherapy in the metastatic setting. There is no limit to number of prior lines of hormonal therapy.
  6. Triple negative breast cancer patients must have progressed on at least 1 cytotoxic therapy in the metastatic setting, with the exception of subjects who progressed within 12 months of adjuvant therapy. However, patients may not have received more than 5 prior lines of cytotoxic chemotherapy in the metastatic setting.
  7. Have measurable disease per RECIST Version 1.1, or bone lesions in the absence of measurable disease (Dose Expansion phase only). Lesions that received radiotherapy are not measurable per RECIST Version 1.1.
  8. Eastern Cooperative Oncology Group (ECOG) performance status of 0 or 1;
  9. Expected survival of more than 12 weeks;
  10. For female patients of childbearing potential and male patients with partners of childbearing potential, agreement to use a highly effective form(s) of contraception, that results in a low failure rate (<1% per year) when used consistently and correctly, starting during the screening period, continuing throughout the entire study period, and for 90 days after taking the last dose of study drug. Such methods include: oral hormonal contraception (combined estrogen/ progestogen, or progestogen-only), associated with inhibition of ovulation together with a barrier method (eg, diaphragm, always containing a spermicide); intrauterine device (IUD), intrauterine hormone-releasing system (IUS), bilateral tubal ligation, vasectomized partner (on the understanding that this is the only one partner during the whole study duration), or sexual abstinence. Oral contraception should always be combined with an additional contraceptive method (ie, barrier method) because of a potential interaction with the study drug. The same rules are valid for male patients involved in this clinical trial

if they have a partner of childbearing potential. Male patients must always use a condom.

A woman is considered to be of childbearing potential if she is postmenarcheal, has not reached a postmenopausal state (ie,  $\geq 12$  continuous months of amenorrhea with no identified cause other than menopause), and has not undergone surgical sterilization (removal of the ovaries and/or uterus).

### 1.1 Exclusion Criteria

Patients will be excluded from the study if **any** of the following criteria is met:

1. **Cohort C only:** patients who have been previously been treated with TAS-102 or regorafenib
2. Absolute neutrophil count (ANC)  $< 1.5 \times 10^9/L$ , platelet count  $< 100 \times 10^9/L$ , or hemoglobin  $< 9.0$  g/dL. Blood transfusion within 1 week prior to enrollment for the purpose of increasing the likelihood of eligibility is not allowed;
3. Serum total bilirubin  $> 1.5 \times$  upper limit of normal (ULN);
4. Alanine aminotransferase (ALT) or aspartate aminotransferase (AST)  $> 1.5 \times$  ULN in patients without hepatic metastases; ALT or AST  $> 3 \times$  ULN in patients with hepatic metastases;
5. Serum potassium, calcium, or magnesium levels out of the normal laboratory reference range, and clinically significant in the investigator's judgment;
6. Creatinine  $> 1.5 \times$  ULN or creatinine clearance  $< 60$  mL/min. Creatinine clearance can either be measured in a 24-hour urine collection or estimated by the Cockcroft-Gault equation as follows:  $CrCl$  (mL/min) =  $[(140 - \text{age}) \times (\text{weight in kg}) \div [72 \times (\text{serum creatinine in mg/dL})]]$  (0.85 if female).
7. Urine dipstick protein  $\geq 2+$  or 24-hour urine protein  $\geq 1.0$  g/24-h. Patients with greater than 1+ proteinuria on urinalysis must undergo a 24-hour urine collection;
8. Uncontrolled hypertension, defined as: systolic blood pressure  $\geq 140$  mmHg and/or diastolic blood pressure  $\geq 90$  mmHg;
9. International Normalized Ratio (INR)  $> 1.5$  or activated partial thromboplastin time (aPTT)  $> 1.5 \times$  ULN, unless the patient is currently receiving or intending to receive anticoagulants for prophylactic purposes.
10. Risk of, or active hemorrhage: history or presence of active gastric/duodenal ulcer or ulcerative colitis, active hemorrhage of an unresected gastrointestinal tumor, history of perforation of fistulas; or any other condition that could possibly result in gastrointestinal tract hemorrhage or perforation within 6 months prior to screening
11. History or presence of hemorrhage from any other site (eg, hemoptysis or hematemesis)

within 2 months prior to screening;

12. History of a thromboembolic event (including deep vein thrombosis [DVT], pulmonary embolism, stroke and/or transient ischemic attack) within 6 months prior to screening;
13. Patients with squamous NSCLC;
14. Clinically significant cardiovascular disease, including but not limited to acute myocardial infarction or coronary artery bypass surgery within 6 months prior to enrollment, severe or unstable angina pectoris, New York Heart Association Class III/IV congestive heart failure, ventricular arrhythmias requiring treatment, or left ventricular ejection fraction (LVEF) <50%;
15. Mean corrected QT interval (QTc) using the Fridericia method (QTcF) >480 msec or any factors that increase the risk of QTc prolongation or risk of arrhythmic events such as hypokalemia, congenital long QT syndrome, family history of long QT syndrome, or unexplained sudden death under 40 years of age in a first-degree relative.
16. Concomitant medications with a known risk of causing QT prolongation and/or torsade de pointes (see list in [Appendix E](#); source list is continuously updated online at [www.qtdrugs.org](http://www.qtdrugs.org));
17. Patients who have ever received a VEGFR inhibitor, **except** for patients with mCRC enrolled in the dose expansion phase;
18. Systemic anti-neoplastic therapies (except for those described in Exclusion 18) or any investigational therapy within 4 weeks prior to the first dose of study drug, including chemotherapy, radical radiotherapy, hormone therapy, biotherapy and immunotherapy;
19. Systemic small molecule targeted therapies (eg, tyrosine kinase inhibitors) within 5 half-lives or 4 weeks (whichever is shorter) prior to the first dose of study drug;
20. Palliative radiotherapy for bone metastasis/lesion within 2 weeks prior to the initiation of study drug;
21. Brachytherapy (ie, implantation of radioactive seeds) within 60 days prior to the first dose of study drug;
22. Use of strong inducers or inhibitors of CYP3A4 within 2 weeks before the first dose of study drug (3 weeks for St John's Wort); P-glycoprotein (P-gp) or breast cancer resistance protein (BCRP) substrate within 2 weeks before the first dose of study drug (see [Appendix F](#) for a list of such medications);
23. Surgery or invasive procedure (ie, procedure that includes a biopsy) within 60 days prior to the first dose of study drug or unhealed surgical incision;
24. Any unresolved toxicities from a previous antitumor treatment greater than

CTCAE v 4.03 Grade 1 (except for alopecia);

25. Known human immunodeficiency virus (HIV) infection;
26. Known clinically significant history of liver disease, including cirrhosis, current alcohol abuse, or active viral hepatitis. For patients with evidence of chronic hepatitis B (HBV), the HBV viral load must be undetectable on suppressive therapy, if indicated. Patients with a history of hepatitis C virus (HCV) infection must have been treated and cured. For patients with HCV who are currently on treatment, they are eligible if they have an undetectable HCV viral load.
27. Evidence of ongoing or active infection requiring intravenous antibiotics;
28. Tumor invasion of a large vascular structure (eg, pulmonary artery, superior or inferior vena cava).
29. Women who are pregnant or lactating;
30. Brain metastases and/or spinal cord compression untreated with surgery and/or radiotherapy, and without clinical imaging evidence of stable disease for 14 days or longer; patients requiring steroids within 4 weeks prior to start of study treatment will be excluded;
31. No other malignancy, except for non-melanoma skin cancer, during the 5 years prior to screening;
32. Inability to take medication orally, dysphagia or an active gastric ulcer resulting from previous surgery (eg, gastric bypass) or a severe gastrointestinal disease, or any other condition that investigators believe may affect absorption of the investigational product;
33. Other disease, metabolic disorder, physical examination anomaly, abnormal laboratory result, or any other condition that investigators suspect may prohibit use of the investigational product, affect interpretation of study results, or put the patient at undue risk of harm based on the investigator's assessment;
34. Known hypersensitivity to fruquintinib or any of its excipients.

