## 6 STUDY VISITS, ASSESSMENTS, AND METHODS

### 6.1 Screening and Pre-treatment Assessments

Written informed consent for participation in the study must be obtained before performing any study-specific screening tests or procedures. Medical history and demographic information, including clinically significant diseases within the previous 5 years, oncology history (including cancer name, primary diagnosis date, stage of diagnosis, prior anti-cancer therapies, and procedures) should be recorded in CRF. Informed consent forms for patients who are not subsequently enrolled will be maintained at the study site. All screening evaluations must be completed and reviewed by the investigator and the clinical monitor to confirm that patients meet all eligibility criteria before the first administration of fruquintinib.

Please see the Study Flowchart provided in [Appendix A](#) for the schedule of screening and pre-treatment assessments. Screening and pre-treatment tests will be performed within 28 days of the first dose of study drug, unless otherwise specified. Results of standard of care tests performed prior to obtaining informed consent and within 28 days prior to study entry may be used (except hematology, coagulation tests, clinical chemistry, or urinalysis results).

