11	Exclusion Criteria This criterion was added.	Page 9 and 37: Exclusion Criteria 16. Patients who have ever received a VEGFR inhibitor.	16. Such drugs are excluded because they target the same molecule as fruquintinib. Patients treated with VEGFR inhibitors previously are unlikely to respond to fruquintinib
12	Page 9 and 38: Exclusion Criteria 16. Systemic anti-neoplastic therapies within 4 weeks prior to the initiation of investigational treatment, including chemotherapy, radical radiotherapy, hormonotherapy, biotherapy and immunotherapy;	Page 9 and 37: Exclusion Criteria 17. Systemic anti-neoplastic therapies (except for those described in Exclusion 18) or other investigational therapies within 4 weeks prior to the first dose of study drug, including chemotherapy, radical radiotherapy, hormonotherapy, biotherapy and immunotherapy;	Note: Original Exclusion Criteria #16 is now #17. 17. Now includes a reference to exceptions to the exclusion criteria based on prior systemic anticancer therapy.
13	Exclusion Criteria This criterion was added.	Page 10 and 37: Exclusion Criteria 18. Systemic small molecule targeted therapies (e.g., tyrosine kinase inhibitors) within 5 half-lives or 4 weeks (whichever is shorter) prior to the first dose of study drug;	Note: Original Exclusion Criteria #18 is now #21 due to added criteria. 18. Small molecule tyrosine kinase inhibitors are an exception to the standard 4-week washout period for prior systemic anti-cancer therapies. Tyrosine kinase inhibitors usually wash out in < 2 weeks; 5 half-lives is expected to be < 4 weeks.
14	Exclusion Criteria This criterion was added.	Page 9 and 37: Exclusion Criteria 20. Brachytherapy (i.e., implantation of radioactive seeds) within 60 days prior to the first dose of study drug.	20. This criterion is added because of the potentially increased risk of severe or serious hemorrhage after brachytherapy.

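### Exclusion criterion 18 exempts drugs described in "Exclusion 18", which is itself; the reference should be to criterion 19 (wrong as written, low severity)

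*Protocol*

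**What the plan says.** The protocol's exclusion list appears in Section 4 (its heading is misprinted as 1.1) and again in the Synopsis. A patient who meets any one criterion is excluded.

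- **Criterion 18** excludes: "Systemic anti-neoplastic therapies (except for those described in Exclusion 18) or any investigational therapy within 4 weeks prior" to the first dose. It goes on to name chemotherapy, radical radiotherapy, and hormonal, biological and immune therapy as included.
- **Criterion 19** excludes: "Systemic small molecule targeted therapies (eg, tyrosine kinase inhibitors) within 5 half-lives or 4 weeks (whichever is shorter") before the first dose.

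The Synopsis carries the same wording and the same two numbers, so both lists print an exception in criterion 18 that refers to criterion 18.

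Appendix K explains how this arose. In Amendment 2 the general washout was criterion 17 and read: "Systemic anti-neoplastic therapies (except for those described in Exclusion 18) or other investigational therapies within 4 weeks prior to the first dose". The small-molecule rule was then criterion 18, so the reference was right. The reason given was: "Small molecule tyrosine kinase inhibitors are an exception to the standard 4-week washout period for prior systemic anti-cancer therapies". The current list opens with a Cohort C rule as criterion 1, covering "patients who have been previously been treated with TAS-102 or regorafenib".

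**The concern.** This is an operative entry rule. It sets how long a patient must have been off previous anti-cancer treatment before the first dose of fruquintinib. An exception that refers to itself has no clear meaning, and each literal way of resolving it departs from the rule the sponsor evidently wanted. One is too strict for small-molecule drugs; the other sets no minimum interval after chemotherapy or a biologic. Sites that follow the words could reach different decisions on the same patient. The SAP also lists protocol deviations with an eligibility category (SAP Section 9), so whether such a patient counts as a deviation would depend on the reading used.

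**Working it through.** The plan gives no figure to reproduce, so the check is a comparison of texts followed by simple logic.

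**Step 1. Is the number really stale?** Appendix K is used here only for history and intent. The exclusion criteria numbered in its Amendment 3 table compare with the current list as follows:

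| Subject | Number in Amendment 3 table | Current number |
|---|---|---|
| INR/aPTT | 8 | 9 |
| Gastrointestinal haemorrhage risk | 9 | 10 |
| Prior VEGFR inhibitor | 16 | 17 |
| Unresolved toxicity | 23 | 24 |
| Liver disease | 25 | 26 |
| Brain metastases | 29 | 30 |

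Each has moved by exactly one. The Amendment 2 pair 17 and 18 has become 18 and 19 in the same way. Only the digit inside the exception stayed put. The defect is visible in the current text alone, so it is not merely a difference from the amendment log.

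**Step 2. What does each reading require?** Let *d* be the days from the last dose of a non-investigational small-molecule targeted drug to the first dose of fruquintinib, and *H* that drug's 5 half-lives in days.

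- *Intended rule (exception points to 19).* Small-molecule drug: excluded if *d* < min(*H*, 28). Other systemic anti-cancer therapy: excluded if given within 28 days.
- *Reading A (circular exception ignored).* Small-molecule drugs fall under criterion 18 as well. Because any one criterion excludes, the patient is out if *d* < 28 or *d* < min(*H*, 28). Since min(*H*, 28) ≤ 28, this reduces to *d* < 28, and the half-life limb of criterion 19 never decides a case. The patients treated differently from the intent are those with *H* ≤ *d* < 28. That band exists whenever *H* < 28, which is what the Amendment 2 rationale expects for these drugs.
- *Reading B (exception applied as written).* Everything in the anti-neoplastic limb of criterion 18 is exempt, so the limb is empty. The stated interval for other systemic anti-cancer therapy falls from 28 days to none. The investigational-therapy limb remains, as do criteria 19 (small molecules), 20 (palliative radiotherapy), 21 (brachytherapy) and 24 (unresolved toxicity).

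**Step 3. Does anything else restore the interval under reading B?** Inclusion criteria 4 to 6 specify which therapies and how many lines a patient must have had. The periods they mention (3 months for treatment failure in Cohorts B and C, 6 months for recurrence after adjuvant therapy in Cohort C, 12 months after adjuvant therapy in triple-negative disease) are upper limits used to define failure or recurrence. None is a minimum gap before the first dose.

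**Step 4. Does it reach the analysis?** The SAP's safety and efficacy sets (SAP Sections 4.2 and 4.4) are defined by dosing, baseline lesions and later tumour status. Criterion 18 does not enter either definition.

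**The case against.** The strongest reply is that no careful reader would be misled. Reading B requires a site to disregard the list of therapies that criterion 18 itself goes on to name. Reading A leaves the exception with nothing to refer to and makes part of the next line pointless. Criterion 19 is the only coherent target, and the Amendment 2 rationale states the purpose outright. There is also a safeguard before dosing: "All screening evaluations must be completed and reviewed by the investigator and the clinical monitor to confirm that patients meet all eligibility criteria". Under reading A, both criteria count back from the first dose, and "Patients will undergo a screening period of up to 4 weeks", so screening can absorb some or all of any extra wait. Under reading B, criterion 24 still excludes patients with unresolved toxicity above Grade 1, alopecia apart.

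All of this stands, and it is why the severity is low. It does not make the text right. Eligibility criteria are applied as written at about 12 sites, and the safeguard is a check against the same faulty sentence.

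A reader might infer that reading A matters only for Cohort B patients who have had regorafenib, because criterion 17 already bars, outside the colorectal expansion cohorts, "Patients who have ever received a VEGFR inhibitor". The documents do not support that limit. Criterion 19 covers every systemic small-molecule targeted drug, not only VEGFR inhibitors, so patients in other cohorts could be affected.

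**Conclusion.** Criterion 18 is wrong as written in Section 4 and in the Synopsis, and the correct target is criterion 19. This rests on the current text and numbering; the amendment history serves only to confirm intent.

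The size is small and cannot be expressed as a number of patients. The documents give no half-lives of earlier drugs, no timing of last doses and no count of patients near the 4-week limit. A reader might take planned expansion enrolment as the group exposed. That is not supported: 6 places in Cohort A and 30 in Cohort B were already planned under Version 3, when the numbering apparently still matched, and the documents do not say how many patients entered under each version.

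A reader might also infer that patients were wrongly delayed, or were dosed without a washout, or that the efficacy results are biased as a result. Nothing in the documents records any such event, and no estimate, sample size or analysis depends on this criterion.

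**What to change.** Inside criterion 18, change "Exclusion 18" to "Exclusion 19", once in Section 4 and once in the Synopsis. Other systemic anti-cancer therapy and investigational therapy then carry a 4-week washout, and small-molecule targeted drugs carry the shorter of 5 half-lives and 4 weeks, as the Amendment 2 rationale intended. The cost is one digit in two places, with no change to intended eligibility, data collection, sample size or analysis.

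If the sponsor wants to know whether the slip had any effect, the planned outputs offer a starting point. SAP Section 12 derives the time from last systemic anti-neoplastic therapy to first dose in months, and 4 weeks is 28/30.4375 = 0.92 months. SAP Section 13.1 lists prior oncology medications by class and preferred term, which may allow small-molecule drugs to be separated from the rest.
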